12.3.3 Analysis of the secondary endpoints

The secondary endpoints overall survival and progression-free survival will be analyzed using Kaplan-Meier-Curves. The 1-year and 2-year survival rates as well as the median survival rate will be provided alongside two-sided 95%- confidence intervals. A Cox

regression frailty model adjusting for the fixed factors treatment and dose, and the frailty factor center will be conducted to compare the two treatment groups.

Missing values in the items of PRO-CTCAE, QLQ-C30 and QLQ-BN20 will be handled as described in the scoring manuals of the QoL measures. Further missing values will be documented and frequencies will be described with descriptive methods.

The secondary endpoint neurocognition (MoCA) will be analyzed using a non-parametric Van Elteren Test stratified for center.

The other secondary endpoints and the patients` characteristics will be displayed by descriptive measures grouped by treatment group. Continuous variables will be described using number non-missing values, mean, standard deviation, median, Q₁, Q₃, minimum and maximum. In addition, t-test between treatment groups will be performed.

For binary or categorical variables absolute and relative frequencies will be provided. Furthermore, two-sided 95%- confidence intervals will be calculated and chi-square tests between treatment groups.

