2.2 Secondary objectives

- incidence of radiation-induced brain injuries > CTC^oII
- progression-free survival
- overall survival
- safety
- patient reported outcome (PRO-CTCAE)
- quality of life (QLQ-C30 and QLQ-BN20)

3 Trial design and schedule

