5.4.1 Patient reported outcome

This trial will assess patient reported outcomes of the common terminology criteria for adverse events (PRO-CTCAE). PRO-CTCAE is a patient-reported outcome measurement

system developed by the National Cancer Institute to capture symptomatic adverse events in patients on cancer clinical trials.

5.5 **Assessment of quality of life**

Quality of life will be assessed prior to radiation, at the end of treatment and during follow-up. Quality of life will be assessed using EORTCs (brain specific) questionnaires for quality of life of cancer patients (QLQ-C30 and QLQ-BN20).

5.6 **Plan for treatment or care after the trial**

After completion of trial treatment, no further adjuvant treatment is scheduled or recommended. Any systemic treatment or chemotherapy or any other treatment applied is not part of the clinical trial.

For tumor progression, treatment alternatives will be evaluated and discussed in the interdisciplinary setting considering options of neurosurgical resection, systemic treatment such as chemotherapy, a second course of radiation therapy, or other.

6 Clinical examinations (trial visits)

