6.1 Overview

Treatment schedule	baseline visit	weekly during RT	end of RT	FU 1 6 weeks post RT	FU 2 3 months post RT	FU 3 6 months post RT	FU 4 9 months post RT	FU 5 12 months post RT	FU 6 15 months post RT	FU 7 18 months post RT	FU 8 21 months post RT	FU 9 24 months post RT
Informed consent	✓											
Inclusion / exclusion criteria	✓											
Demographic information	✓											
Anamnesis/ clinical examination	✓			✓	✓	✓	✓	✓	✓	✓	✓	✓
randomization	✓											
AEs und SAEs	✓	✓	✓	✓	✓	✓	✓	✓	✓	✓	✓	✓
Symptoms/toxicity	✓	✓	✓	✓	✓	✓	✓	✓	✓	✓	✓	✓
MRI	✓			✓	✓	✓	✓	✓	✓	✓	✓	✓
QLQ-C30 & QLQ-BN20	✓		✓			✓		✓				✓
PRO-CTCAE	✓	✓	✓	✓	✓	✓	✓	✓	✓	✓	✓	✓
(Cognitive assessment)	✓		✓			✓		✓				✓

The number of trial visits and the extent of their examinations is equivalent to standard care. Trial related additional expense is a result of the neurocognitive testing. The MoCA test is designed to take less than 15 min. Completing the PRO-CTCAE form takes less than 5 min. Additional time is needed for completing the quality of life questionnaires which takes approx. additional 20 min per visit. In total, the additional time expense for the patient sums up to 40 min on five trial visits and 5 min at the remaining visits.

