6.2 Base line examination

- Anamnesis and clinical examination
- Assessment of QoL
- Assessment of toxicity (CTCAE)
- Assessment of patient reported outcome (PRO-CTCAE)

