12.3.5 Homogeneity of the intervention groups

The homogeneity of the treatment groups will be described by comparison of the demographic data and the baseline values.

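### Quality-of-life scores are compared by a t-test without baseline score or center, and MoCA by a van Elteren test without baseline, so precision is given away

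*Protocol*

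**What the plan says.** Section 12.3.3 of the Protocol names the tests for the secondary endpoints.

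- **Survival endpoints:** Kaplan-Meier curves and a Cox frailty model with treatment, dose and center.
- **MoCA:** "The secondary endpoint neurocognition (MoCA) will be analyzed using a non-parametric Van Elteren Test stratified for center".
- **Everything else:** "The other secondary endpoints and the patients` characteristics will be displayed by descriptive measures grouped by treatment group". For continuous variables it then adds: "In addition, t-test between treatment groups will be performed".

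QLQ-C30 and QLQ-BN20 are listed as secondary objectives in section 2.2 and are given no other between-group test, so they fall in the third group. The synopsis mentions only descriptive measures for that group and no t-test.

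Baseline quality of life is planned: "Quality of life will be assessed prior to radiation, at the end of treatment and during follow-up" (section 5.5), and section 6.2 lists "Assessment of QoL" at the baseline examination. The visit tables tick both the quality-of-life questionnaires and the cognitive assessment at baseline, end of radiotherapy, and 6, 12 and 24 months; the cognitive row is in brackets. The only stated use of baseline values is in section 12.3.5: "The homogeneity of the treatment groups will be described by comparison of the demographic data and the baseline values".

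**The concern.** The baseline score is usually the strongest single predictor of a later score on the same questionnaire or cognitive test. Leaving it out keeps avoidable between-patient variance in the comparison, and any chance difference between the arms at baseline passes partly into the estimated treatment difference. The t-test also leaves out center, although section 12.4.1 stratifies randomization by it.

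The choice sits oddly with the rest of the protocol. Section 11 expects prognostic covariates to raise the power of the primary analysis, and both the primary model and the Cox model adjust for dose and center. Section 1.3 justifies avoiding lesions partly by their possible effect on quality of life and neurocognitive performance, so these comparisons bear on how the primary result will be interpreted. Their precision is set by a sample size chosen for lesion counts.

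**Working it through.** **Inputs from the Protocol.** 49 patients per group evaluable and 60 per group enrolled (section 11); two centers; the tests as named in section 12.3.3.

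**Assumptions, not in the Protocol.** Correlation r between baseline and follow-up score, taken as 0.3, 0.5 and 0.7; equal SD at both times; two-sided 5% level; 49 per group also evaluable for these endpoints.

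**1. The plan's own sample size.** No power or precision is stated for quality of life or MoCA, so the figure to reproduce is the one that fixes their group size. With event rates 0.86 and 0.18 and dispersion 0.2597:

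n per arm = (1.960 + 0.842)² × (1/0.86 + 1/0.18 + 2/0.2597) / [ln(0.18/0.86)]² = 46.3, against 46 stated.

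The unrounded experimental rate of 0.1771 gives 45.6, hence 46. Dropout: 98 / (1 − 0.18) = 119.5, hence 120. The group sizes reproduce.

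**2. Variance of the treatment comparison**, relative to a t-test on the follow-up score:

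- t-test on follow-up score: 1
- t-test on change from baseline: 2(1 − r)
- ANCOVA on baseline: 1 − r²

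ANCOVA relative to the change score: (1 − r²) / [2(1 − r)] = (1 + r)/2.

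| | r = 0.3 | r = 0.5 | r = 0.7 |
|---|---|---|---|
| Factor, t-test on change | 1.40 | 1.00 | 0.60 |
| Factor, ANCOVA | 0.91 | 0.75 | 0.51 |
| ANCOVA variance cut against follow-up score | 9% | 25% | 49% |
| ANCOVA variance cut against change score | 35% | 25% | 15% |
| Interval width against follow-up score, √(1 − r²) | 0.95 | 0.87 | 0.71 |
| Sample-size equivalent, 1/(1 − r²) | 1.10 | 1.33 | 1.96 |

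**3. Detectable difference and power, 49 per group.** The difference detectable with 80% power is (1.960 + 0.842) × √(2 × factor / 49). The t-test on the follow-up score gives 0.57 SD; ANCOVA gives 0.54 / 0.49 / 0.40 SD. Power for an illustrative 0.5 SD difference rises from 70% to 74% / 82% / 93%. With 60 per group it rises from 78% to 82% / 89% / 97%.

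**4. Chance imbalance.** The SD of a chance baseline difference is √(2/49) = 0.20 SD units, so its 95% range is ±0.40 SD. A share r of it enters an unadjusted comparison: at the edge of that range, 0.12 / 0.20 / 0.28 SD.

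**5. Simulation** (4,000 trials per setting, two centers, 49 per group, normal scores):

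- With no true difference, the rejection rate was between 4.1% and 5.1% for all methods.
- With a 0.5 SD difference, the van Elteren test had power of about 67% / 66% / 68%. On baseline-adjusted ranks it had 69% / 75% / 89%. ANCOVA had 74% / 80% / 93%.
- In trials with a baseline difference above 0.3 SD, the t-test estimate was off by 0.11–0.13 / 0.19–0.22 / 0.26–0.28 SD, and ANCOVA by at most 0.015 SD.

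**The case against.** **This is SAP detail.** The protocol names test families and defers further details to a SAP that is not shown. It does not say whether the follow-up score or the change from baseline is tested, nor at which visit. That is fair, and it is why both variance comparisons are given. A reader might infer that the plan ignores baseline and the repeated visits altogether; silence on the outcome variable and visit does not show that. But the protocol itself chooses the test, and a t-test on either variable is less precise than ANCOVA at each correlation shown.

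**The comparisons are only supportive.** Quality of life comes under the t-test sentence by elimination, the synopsis offers description only, and no alpha is allocated. This limits the consequences but does not make the less precise test preferable.

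**The gain may be small.** At r = 0.3 it is 9% of variance against the follow-up score, and the simulated MoCA power moves only from about 67% to 69%. That stands.

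**Baseline MoCA is less certain than baseline quality of life.** Its row is bracketed in the visit tables, and it is absent from the baseline list in 6.2 and from the objectives in 2.2. In its favor, section 6.1 says "In total, the additional time expense for the patient sums up to 40 min on five trial visits", and 15 (MoCA) + 5 (PRO-CTCAE) + 20 (quality of life) = 40 minutes; the tables tick five such visits, baseline among them. Baseline MoCA is therefore probably intended, but one should not assume that every patient will have it.

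**Conclusion.** The point holds as a loss of efficiency in named secondary analyses. Against a t-test on the follow-up score, the avoidable variance is 9% / 25% / 49% at r = 0.3 / 0.5 / 0.7; against a t-test on change it is 35% / 25% / 15%. The size rests on the assumed correlation. The direction does not, provided the baseline score is predictive. The change is worth making, and the primary conclusion is unaffected.

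Three stronger readings are not supported:

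- **That the tests are invalid.** Type I error is preserved over randomizations. The distortion arises only in trials that happen to be imbalanced at baseline.
- **That chance baseline differences are large relative to a plausible effect.** The protocol gives no expected effect and no SD for quality of life or MoCA, so this ratio cannot be formed.
- **That the MoCA test ignores the design.** It is stratified for center; only the baseline value is missing.

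**What to change.** Edit section 12.3.3 and carry the change into the SAP and the synopsis, which at present mentions no t-test:

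- **QLQ-C30 and QLQ-BN20:** replace the t-test by ANCOVA at each follow-up visit, or by a mixed model for repeated measures, with treatment, baseline score and center. Prescribed dose may be added to match the primary model.
- **MoCA, where the baseline value is available:** use the same model, or a van Elteren test on baseline-adjusted ranks stratified by center. A van Elteren test on simple change from baseline is not a remedy. By the variance factor 2(1 − r), change gains nothing at r = 0.5 and is less precise than the follow-up score below that.
- **Baseline MoCA:** if it is intended for all patients, list it in section 6.2.

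The quality-of-life change needs no new patients, visits or data. The cost is a protocol edit as well as SAP text, because the protocol names the tests. It should be made before any unblinded results are seen.

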8.1 Adverse events

According to GCP, an adverse event (AE) is defined as follows: Any untoward medical occurrence in a subject administered a pharmaceutical product or treatment and which does not necessarily have a causal relationship with this treatment. An AE can therefore be any unfavorable and unintended sign (including an abnormal laboratory finding), symptom, or disease temporally associated with the use of a medicinal (investigational) product or treatment, whether or not related to the medicinal (investigational) product.

An AE may be:

- New symptoms/ medical conditions
- New diagnosis
- Changes of laboratory parameters
- Intercurrent diseases and accidents
- Worsening of medical conditions/ diseases existing before clinical trial start

- Recurrence of disease
- Increase of frequency or intensity of episodical diseases.

A pre-existing disease or symptom will not be considered an adverse event unless there will be an untoward change in its intensity, frequency or quality. This change will be documented by an investigator. Each AE developing during study treatment or within 30 days after completion of study treatment should be documented up to 6 months after completion of study treatment. The investigator is responsible to perform and consider all required therapeutic measures and methods to follow-up this condition. An event, which occurs in conjunction or association with tumor progression will not be considered an AE or subsequently as an SAE unless more severe than expected.

Following examples will also not be considered as an AE:

- A medical or surgical procedure (the condition that led to the procedures is an AE)
- Situations in which an untoward medical occurrence did not occur (e.g. social and/or convenience admission to a hospital)
- Anticipated day-to-day fluctuations of pre-existing disease(s) or conditions(s) present or detected at the start of the study that do not worsen
- The disease/disorder being studied or expected progression, signs or symptoms of the disease/disorder being studied, unless they are more severe than expected for the subject's condition

The grading of AEs in this trial will be carried out on the basis of the 5-grade scale as defined in CTCAE v5.0:

Grade 1	mild AE
Grade 2	moderate AE
Grade 3	severe AE
Grade 4	life-threatening AE or AE causing disablement
Grade 5	death related to AE

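### Section 12.3.3 has no rule for ordered outcomes, so PRO-CTCAE responses, if analysed as categories, go to a chi-square test that ignores their order and loses power

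*Protocol*

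**What the plan says.** Protocol section 12.3.3 assigns methods to the secondary endpoints by type.

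- Overall and progression-free survival have Kaplan-Meier curves and a Cox frailty model with center.
- MoCA has its own rule: "The secondary endpoint neurocognition (MoCA) will be analyzed using a non-parametric Van Elteren Test stratified for center".
- The remaining secondary endpoints "will be displayed by descriptive measures grouped by treatment group". Continuous variables also get a t-test between arms.
- For the rest: "For binary or categorical variables absolute and relative frequencies will be provided". The next sentence adds: "Furthermore, two-sided 95%- confidence intervals will be calculated and chi-square tests between treatment groups".

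There is no separate rule for ordered categories, and neither the t-test nor the chi-square test is stratified. Randomisation is stratified by center (section 12.4.1).

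Section 2.2 lists PRO-CTCAE as a secondary objective. The visit schedule (section 6.1) collects it at baseline, weekly during radiotherapy, at the end of radiotherapy and at all nine follow-up visits. Beyond the general rules, section 12.3.3 mentions PRO-CTCAE only for missing items.

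**The concern.** Patient-reported symptom items are graded answers. A Pearson chi-square test gives the same result however the levels are arranged. It therefore spreads its power over every possible difference between two distributions, when the difference of interest is a shift towards milder or worse answers. A rank test concentrates on that shift with one degree of freedom.

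The protocol accepts this reasoning elsewhere. It uses the van Elteren test for MoCA and again in a sensitivity analysis of the primary endpoint (section 12.3.2), and gives no reason for treating ordered patient-reported toxicity differently.

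At stake is the reading of one secondary objective. The primary endpoint is an imaging finding, and section 1.3 speaks of asymptomatic treatment-related changes on MRI. PRO-CTCAE is one of the measures, with quality of life and MoCA, that can show whether patients notice a difference. With about 50 to 60 per arm, an inefficient test can make a real shift look like no difference.

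**Working it through.** **Inputs from the protocol.** The protocol states no power for any secondary endpoint, so there is no figure of that kind to reproduce. The arm sizes are those of section 11: 98 patients (49 per arm) before drop-out. The inflated number reproduces: 98 / (1 − 0.18) = 119.5, hence 120 (60 per arm).

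**Assumptions.** The protocol gives neither the number of PRO-CTCAE response levels nor a distribution, so both were varied. The level of the chi-square tests is not stated; two-sided 5% is taken, in line with the two-sided 95% intervals.

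**Step 1: which outcomes the rule reaches.**

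| Outcome | Rule in the protocol | Is order lost? |
|---|---|---|
| MoCA | van Elteren by center (12.3.3) | no |
| PRO-CTCAE items | no rule of their own; chi-square if categorical, t-test if continuous (12.3.3) | yes, if categorical with more than two levels |
| Brain injury above grade II | binary (2.2); chi-square | no order to lose |
| AE and SAE grades | descriptive with 95% intervals (12.3.4) | no between-arm test |

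**Step 2: analytic check.** An ordered 1-df test has 80% power at noncentrality (1.960 + 0.842)² = 7.85. If the effect is a pure shift, the chi-square test on k levels has about the same noncentrality on k − 1 degrees of freedom. Its power is the chance that a noncentral chi-square (k − 1 df, 7.85) exceeds the 5% critical value.

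| Levels | df | Critical value | Power | Loss (points) |
|---|---|---|---|---|
| 2 | 1 | 3.841 | 80.0% | 0 |
| 3 | 2 | 5.991 | 70.9% | 9.1 |
| 4 | 3 | 7.815 | 64.5% | 15.5 |
| 5 | 4 | 9.488 | 59.5% | 20.5 |

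**Step 3: simulation.** 20,000 data sets per case, two centers of about equal size, no center effect. The odds of being at or below each level are multiplied by a common odds ratio (OR) in one arm. Entries are power of chi-square v van Elteren, in %.

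| Control distribution (%) | Per arm | OR 2 | OR 2.5 | OR 3 |
|---|---|---|---|---|
| 20/20/20/20/20 | 49 | 28.7 v 47.7 | 48.1 v 70.3 | 65.9 v 85.0 |
| | 60 | 35.4 v 56.6 | 58.0 v 78.9 | 75.8 v 91.4 |
| 40/25/20/10/5 | 49 | 25.1 v 44.9 | 41.8 v 65.5 | 58.5 v 80.4 |
| | 60 | 31.3 v 52.8 | 51.9 v 75.1 | 69.1 v 88.0 |
| 60/20/12/6/2 | 49 | 19.4 v 36.4 | 31.6 v 54.5 | 43.4 v 67.9 |
| | 60 | 24.3 v 43.6 | 40.2 v 63.9 | 53.1 v 76.7 |
| 40/30/20/10 | 49 | 29.4 v 44.2 | 47.7 v 65.9 | 63.9 v 80.2 |
| | 60 | 34.8 v 51.4 | 57.8 v 74.9 | 74.1 v 87.2 |
| 50/30/20 | 49 | 32.2 v 40.6 | 50.5 v 60.8 | 64.8 v 74.4 |
| | 60 | 38.0 v 48.4 | 60.0 v 70.1 | 74.8 v 83.2 |

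The gap is 16 to 25 points with five levels, 13 to 18 with four and 8 to 10 with three. With five levels it is 8 to 10 points at OR 1.5 and 6 to 22 at OR 4. Over all cases with more than two levels and OR 1.5 to 4, it runs from about 4 to 25. With no effect, the van Elteren test rejects in 4.8 to 5.2% of runs and chi-square in 4.0 to 5.2%, so the gain is not bought with false positives.

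**Step 4: how much is due to center.** Without a center effect, the unstratified Wilcoxon and van Elteren tests agree within 0.3 points. Stratification adds about 1 point at a center OR of 2 and 2 to 3 points at a center OR of 3.

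**Step 5: two alternatives.** For a binary outcome (70/30, 49 per arm, OR 2), chi-square has 30.0% and van Elteren 29.9%, so nothing is lost. If item levels were scored as numbers and compared by t-test, a simulation of the same settings without centers shows a loss of about 0 to 6 points against the Wilcoxon test, largest for the 60/20/12/6/2 distribution.

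**The case against.** The strongest case against is that section 12.3.3 never calls PRO-CTCAE categorical, presents these endpoints descriptively and attaches no hypothesis, power or success criterion to the tests. The synopsis lists only descriptive measures for them. The chi-square test is valid, and an SAP that is not shown could name an ordinal test.

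Much of this stands. The point concerns efficiency, not validity, and depends on how the items are handled. But section 12.3.3 is not silent: it names a between-arm test for each type of variable, and an SAP that follows it would carry an order-blind test forward for graded answers.

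Four stronger readings are tempting, and the protocol does not support them.

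- *CTCAE grades are affected too.* A reader might infer this from section 8.1, where "The grading of AEs in this trial will be carried out on the basis of the 5-grade scale as defined in CTCAE v5.0". That passage defines a scale and names no test. Section 12.3.4 makes the AE analysis descriptive, and the CTCAE-based secondary endpoint, "incidence of radiation-induced brain injuries > CTC^oII", is binary.
- *About 20 points are lost in general.* That holds for five levels, a consistent shift and moderate effects. The protocol states none of these.
- *Ignoring center is a large part of the loss.* Step 4 shows that it is not.
- *The trial's main result is at risk.* The confirmatory analysis in section 12.3.2 is a separate model and is untouched.

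**Conclusion.** The point holds in a limited form. Section 12.3.3 lacks a rule for ordered variables, and its rule for categories would discard the order of PRO-CTCAE responses. The cost is about 16 to 25 points of power with five levels, 13 to 18 with four, 8 to 10 with three and none with two.

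These figures assume 49 to 60 evaluable patients per arm, proportional odds with a common odds ratio of about 2 to 3, two-sided 5% and the distributions shown. If the intervention changed the answers in a way that is not a shift in one direction, the rank test's advantage would shrink or vanish. If the items were analysed as continuous scores, the t-test rule would apply and the loss would be small.

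This is an almost free improvement to a secondary analysis, not an error that threatens the trial.

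**What to change.** In section 12.3.3, state that PRO-CTCAE items are analysed as ordered outcomes and compared with the van Elteren test stratified by center, or with a proportional-odds model that includes center. The model also gives an effect estimate with a confidence interval, which suits the descriptive purpose. Keep the chi-square test for binary or unordered variables. No change is needed for CTCAE grades.

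The cost is one or two sentences in the protocol or SAP, with no new data and no extra patients. Make the change before database lock, so that the test is not chosen after the results are seen.
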